### **Common reasons for Inpatient Admission for fiscal year 2019:**

Reasons for Admission	Number of Veterans
Acute Rehabilitation	~87
Annual Evaluation (chronic SCI)	~368
Wound Care	~269
Respite Care	~154

### **Common reasons for outpatient visits in fiscal year 2019:**

Reasons for Visit	Number of Veterans
Annual or new evaluation (chronic SCI)	472

The recruitment for the proposed study will be drawn from the SCI population within the Richmond catchment area (this includes Veterans who live outside Richmond but use CVVHCS for their SCI yearly evaluation). After informed consent, each participant will undergo a complete physical examination to be done by the PI or a board-certified Physiatrist. The physical examination will include:

1. General: Race, gender, mood
2. Vital signs:

- a. Temperature
- b. Pulse
- c. Respiration rate
- d. Pulse oximetry
- e. Blood Pressure
- f. Pain level
- g. weight

3. Skin inspection for:
  - a. Rashes
  - b. Eruptions
  - c. Pressure sores
4. Head, Eyes, Ears, Nose, and Throat (HEENT)
  - a. Head-size and shape; tenderness
  - b. Eyes-conjunctiva; sclera, pupil size, shape and reactivity; extraocular muscle movements; visual fields
  - c. Ears-hearing test, tenderness, discharge, external canal, tympanic membrane.
  - d. Nose-symmetry; palpation of sinuses for tenderness; flaring; grunting
  - e. Throat-lips, teeth, gums, tongue, pharynx
5. Neck:
  - a. Range of motion; tenderness, jugular vein distension, lymph nodes, thyroid, carotid bruits, Hepatojugular reflux
6. Chest:
  - a. Symmetry of movement with respiration
  - b. Palpation for tenderness
  - c. Breath sounds
7. Heart:
  - a. Rate
  - b. Palpation of precordium for point of maximal impulse and thrill
  - c. Auscultation for heart murmurs
8. Abdomen:
  - a. Shape
  - b. Auscultation for bowel sounds and bruits
  - c. Percussion for tympanic masses
  - d. Palpate for tenderness/guarding; organomegaly
9. Genitalia:
  - a. Inspect for lesions, swelling, masses, hernias
10. Rectal:
  - a. Inspect/palpate for hemorrhoids, fissures, tags, sphincter tone
  - b. Note presence or absence of stool
  - c. Male- prostate size and texture, nodularity, tenderness
11. Musculoskeletal:
  - a. Range of motion
  - b. Absence of limbs/deformities
  - c. Swelling
  - d. tenderness

12. Neurological assessment:

- a. Mental status
- b. Cranial nerves
- c. motor strength and sensory level based on the International Standards for Neurological Classification of Spinal Cord Injury (ISNCSCI), to determine level of motor and sensory impairment.
- d. Reflexes
- e. Modified Ashworth scale (measure of spasticity)
- f. Penn Spasm Frequency Scale (self-reported measure of perceived frequency and severity of spasticity).

Eligibility to participate will be based on physical examination findings. Body weight will be measurement using a wheelchair weighing scale and subtracting the wheelchair weight from the total weight to obtain participants' absolute weight. A baseline electrocardiogram (ECG) to rule out any concerning abnormal heart rhythm or myocardial ischemia will be obtained. All participants will also undergo bone mineral density (BMD) measurements using Dual-energy X-ray absorptiometry (**DXA**) focusing on the distal femur and proximal tibia and MRI using a 3 Tesla magnet (GE) to determine skeletal muscle and cortical bone CSAs (specific Aim 1) and fasting blood work (specific Aim 2), at no cost.

**Inclusion criteria.** To be included, participants will have to:

1. Be 18-65 years of age
2. Have history of traumatic SCI ( $\geq$ 1-year) with NLI of C8-T10 and AIS A or B (confirmed by AIS examination performed by PI or a qualified Provider).
3. Have a caregiver who is available and willing to be trained to apply intervention protocol in the home (placing weights and positioning the Veteran) throughout study duration
4. Be a wheelchair user for primary mode of mobility
5. Have Knee extensors that must respond to standard surface electrical stimulation procedures (stimulation frequency procedures, 30 Hz; pulse duration:1 ms and amplitude of the current of less than200 mA)).
6. Be able to receive written clearance from their medical Providers to ensure safety of participants.
7. **Be a Veteran (male or female),** however, the Department of Veteran Affairs has limited number of female Veterans, especially those with motor complete injury at level C8-T10 (currently, there are only 3 female Veterans with the target NLI in our SCI registry). Hence, inclusion of women Veterans may be challenging due to this disparity in the SCI population. If we fail to recruit 20 Veterans, we may seek an IRB approval to recruit non-Veterans to meet our target sample size.
8. Have normal ECG
9. Commit to undergo 9 months of trial; 4.5 months of open-kinematic chain resistance training followed by 4.5 months of closed-kinematic chain using simple rowing approach + Vit. D supplementation (Experimental group) **or** 9 months of passive movement +Vit D supplementation (control group).

**Rationale for conducting the trial up to 9 months:**

The preliminary study of Veterans with motor complete injury demonstrated that 16 weeks (i.e. 4 months) of surface Neuromuscular electrical stimulation (NMES) evoked resistant training (RT) impacted skeletal muscle size positively, which will convey skeletal loading benefits to the bones. Additionally, the increase in muscle mass has the potential to increase peripheral blood flow and increase blood glucose uptake that may delay the onset of Type 2 diabetes or/and improve diabetes control for those who are already diabetic. However, the 16 weeks study was only exploratory and bone adaptation are likely to take longer time period, especially in persons with SCI. The primary rationale was that the duration of previous work that effectively used either electrical stimulation or Vit D ranged from 6 to 12 months. Since we are unaware of any study that has determined the combined effects of both interventions, we chose to average 6 and 12 months to arrive at a 9 months trial. We believe that compared to the initial exploratory trial for 4 months, the proposed 9 months trial will set the basis for future clinical trials that are adequately powered to enhance bone parameters in persons with chronic SCI.

**Rationale for recruitment outside Richmond and non-Veterans:**

The target population for this study is Veteran with SCI but are no different than SCI individuals in the general population. Therefore, in the event, that we are unable to meet the target sample size within study period, we may reach out to Virginia Commonwealth University (VCU), as previously discussed.

**Inclusion of women Veterans:**

There is inherently gender disparity in the Veteran population based on the fact that more men than women tend to join the military. However, the study team will make every effort to recruit female Veterans but may be limited due to scarcity of female Veterans with SCI.

**Exclusion criteria:** Every effort will be made to ensure participants' safety and any participant with active medical condition that may confound the result of the trial will be excluded from participation.

Potential participants will be excluded if they exhibit any of the following:

1. Neurological injury other than SCI
2. Older than 65 years of age as they may likely have considerable amount of bone loss at that age.
3. Have severe osteoporosis because loading porous/fragile bone by electrical stimulation may result in bone fracture.
4. Those classified as AIS C & D, as they may already be engaging in weight bearing activities that may confound the results of this trial.
5. Unhealed or unstable fractures in either lower or upper extremities.
6. Severe scoliosis, deformities in the hip, knee, or ankles OR impaired range-of-motion, as these could be a barrier to safe positioning on the rowing machine, and on MRI or DXA tables.
7. No caregiver or family member/significant other, willing to help with placing weights and positioning participants' lower extremities on the rowing machine.

8. Untreated or uncontrolled hypertension (systolic blood pressure (BP) > 140 mmHg; diastolic BP > 90 mmHg), and/or sudden hypotension upon transferring from bed to wheelchair, characterized by a drop in BP by 20 mmHg (especially in persons with tetraplegia) or heart rate > 100 beats per minute.
9. Anti-coagulation or anti-platelet therapy (including aspirin)
10. Implanted pacemakers, implanted defibrillator devices or any metallic implants including knee or hip implants.
11. Presence of bullets in vertebral column or shrapnel anywhere in the body that may interfere with MRI procedure.
12. Other medical conditions including cardiovascular disease, uncontrolled type II DM, active deep vein thrombosis (DVT), uncontrolled autonomic dysreflexia, use of insulin for DM management, pressures injuries of stage 3 or higher, or active urinary tract infection.
13. Severe hypercalcemia (serum calcium > 16mg/dl), stage III-V kidney disease, post-menopausal or estrogen dependent female, and men undergoing anti-androgen therapy or are post orchiectomy.
14. DXA total body T-score less than -2.5. Total hip BMD T-scores < -3.5 and knee BMD scores of less than 0.6 g/cm^2.
15. Untreatable severe spasticity bearing on potential participants' activities of daily living, such as transfers from bed to wheelchair or maintaining position in wheelchair.
16. Any psychiatric illness confounding judgment or cognitive impairment in participant or caregiver who is expected to help participant in the trial.
17. Those with prosthetic lower limbs
18. Any condition that, in the judgment of the PI or other medical Providers, preclude safe participation in the study and/or has the potential to expose/increase participant's risk of infection.
19. Unable to tolerate increasing either electrical stimulation current or weights to the lower legs for any reason.

**Sources of Materials:**

Electronic medical records (EMR) will be reviewed for each potential participant enrolled by IRB-approved investigators (PI or Co-PI; [name] and [name], respectively). All research data will be stored in the PI's office in a locked cabinet. No VA research data will be destroyed.

**II. Study Procedures:**

The study procedures include: consenting process, description of study activities and expectations. Consent to participate will be obtained as described under process of obtaining informed consent. Informed consent will be obtained prior to enrollment in the study. After consenting, the participant will undergo 1-hour of history and physical examination that will be done by the PI or a certified SCI physician ([name]) at CVVHCS. The screening examination will include history and physical examination and assessment of inclusion/exclusion criteria previously stated.

**Detailed Strategies for the Recruitment Plan.**

Efforts will be made by the applicant (PI), to implement a successful recruitment plan, and to avoid any source of coercion during the actual process. Twenty Veterans (10 in

intervention group vs. 10 in control group) with motor complete SCI involving C8-T10 and AIS A or B classification, will be recruited to participate in a 9 months trial. The primary goal of this work is to ensure that our procedures are safe and effective for persons with motor complete SCI.

The following timeline will be implemented to meet our recruitment goals. We plan to recruit 20 Veterans/non-Veterans over a 2-year period (24 months). We plan to start participants enrollment in the 1st quarter of year-1 and finish in 1st quarter of year-2 (see recruitment table below). We will continue to collect data and finish analysis by the 4th quarter of year two. This is feasible considering our previous experience recruiting for the parent study. Also, we do not anticipate attrition due to prior established compliance with telehealth home-based study. We plan to offer resistant training to participants on a flexible schedule so as to accommodate their lifestyle, to avoid attrition. Participants will be randomized to either intervention or control group.

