**Pitfalls and Alternatives:** Changes in trabecular bone parameters may be indeterminate because of the smallness and heterogeneity of sample size. We will rely on previous experience to calculate the effect size, and on that basis, adequately power future trials. **Failure to recruit proposed sample size:** The applicant's primary mentor ([name]) successfully conducted similar clinical trials in the past and demonstrated that use of telehealth facilitated recruitment and compliance among Veterans with SCI. Additionally, we may recruit non-Veterans to ensure completion of the study within the proposed timeline. [name] has a dual appointment with VCU and can successfully collaborate with VCU to ensure recruitment of the target sample size.

**Statistical Analyses.** After signing consent, the PI will randomly assign a number from 1-20 to participants using a computer program (nQuery). The order of enrollment will determine the participant's number based on level and duration of injury. Summary of information, including means and SD, frequencies and percentages, for all study variables will be calculated at all-time points. T-tests and Pearson chi-square tests will be used to compare characteristics that may act as confounders, including age, level and time since injury.

**Sample Size Justification:** Being a pilot study, consideration of sample size is just to allow determination and examination of preliminary evidence of efficacy and effect size estimation towards a larger future randomized trial. The proposed sample size of 10 per group is adjudged sufficient to accomplish these goals. Although Julious recommends a sample size of at least 12 per group on the basis that gain in precision for estimates of variance becomes relatively small on reaching a sample size of 12, we are unable to meet that target because of cost of the intervention and testing. Our sample size still allows for adequate accuracy. As shown in **Fig 6**, the gain in precision is still limited with a sample size of 10 per group. Although testing efficacy is not the primary goal, we will have 80% power to detect a standardized mean difference of  $d=0.9$  using an alpha of 0.25 corresponding to a large effect size. Type I error rates larger than 0.05 are often used and recommended for pilot studies where tests of efficacy are not the primary aim.

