**Data Analysis Plan:** IBM SPSS statistical software version 26 will be used. Being a pilot study, primary analyses will be mainly descriptive. Means and SD will be estimated for utilization (number of sessions completed), with each outcome. Finally, analysis of covariance (ANCOVA) will be used to test differences between groups post intervention for each outcome, using the baseline score as a covariate. If normality of groups appears to be violated in the sample normalizing transformations or non-parametric statistics will be considered.

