**Adverse Events:**

All participants will be monitored for any changes in health status from baseline. The SCI Provider on record for each participant will be notified of any changes that may require attention. An adverse event is any experience that has taken place during research project, which, in the opinion of the investigators, was harmful to the research participant, increased the risks of harm in the research, or had an unfavorable impact on

the risk/benefit ratio. Adverse events will be monitored throughout the study period via physical examinations, vital signs, laboratory tests, review of medical charts, and verbalized concerns by the participants, caregivers, significant other or family member. Any adverse event will be documented in each participant's file. Files will be reviewed for adverse events, protocol violations, and reasons for dropouts/withdrawals every ten days. The PI will provide CVVHCS IRB an annual summary of adverse events. All serious adverse events (SAEs), such as those that are life-threatening or involve hospitalization, will be promptly reported to CVVHC IRB Research Subjects Protection Program. Serious adverse event is defined as the unexpected medical occurrence associated with the research procedure that may lead to death, life-threatening medical condition, inpatient hospitalization for or longer than 24 hours, persistent or significant incapacity or substantial disruption of the ability to engage in normal activities of daily living.

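### The stated primary goal of ensuring safe and effective procedures conflicts with the pilot rationale and cannot be met with 10 treated participants, and adverse-event counts rest on the opinion of investigators who know the arm

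*Combined protocol and SAP*

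**What the plan says.** **Goal.** The Human Subject Section, under Detailed Strategies for the Recruitment Plan, states: "The primary goal of this work is to ensure that our procedures are safe and effective for persons with motor complete SCI". The same section plans 20 participants, 10 in the "intervention group vs. 10 in control group", followed for nine months with no attrition expected.

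**Purpose of the sample size.** The Sample Size Justification gives the purpose as determination and "examination of preliminary evidence of efficacy and effect size estimation towards a larger future randomized trial". It adds: "The proposed sample size of 10 per group is adjudged sufficient to accomplish these goals". It also says "Although testing efficacy is not the primary goal". Aim 1 concerns bone micro-architecture and Aim 2 bone biomarkers. Neither is a safety aim.

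**Analysis.** The Statistical Analyses paragraph promises descriptive summaries of every study variable. The Data Analysis Plan is mainly descriptive: "Means and SD will be estimated for utilization (number of sessions completed), with each outcome". ANCOVA with the baseline score as covariate follows for each outcome. Neither paragraph names adverse events, fracture, falls, autonomic dysreflexia or skin injury.

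**Capture of events.** The Adverse Events section defines an adverse event as an experience "which, in the opinion of the investigators, was harmful to the research participant", or that in their view raised the risk of harm or worsened the risk/benefit balance. The principal investigator performs the randomization (Statistical Analyses) and supervises the stimulated training by telehealth (Resistance training).

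**The concern.** Two parts of one document give different primary purposes. One is to ensure safety and effectiveness. The other is to obtain estimates for a later trial, with efficacy testing expressly secondary. A reader of the final report could measure the trial against either.

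The safety half of the goal has no counterpart in the statistical sections: no safety aim, no named safety outcome, no statement of precision and no criterion for calling the procedures safe. Yet Risk to Subjects itself lists fracture, falls, dysreflexia and skin injury as the hazards of the intervention.

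The definition of an adverse event adds a measurement problem. Whether an experience counts depends on an opinion about harm, and the principal investigator forms that opinion knowing the assignment. A fall without injury during a transfer to the rowing machine, and a similar fall in a control participant's home, could be classed differently. What is at stake is whether the counts can be compared between arms and carried into the design of the larger trial.

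**Working it through.** **Inputs**
- 10 per arm, 20 in total (Detailed Strategies for the Recruitment Plan; Sample Size Justification).
- Vitamin D is given to all 20 (Vit D section).
- Rowing occupies only the second 4.5 months (Resistance training).
- Zero events is a scenario chosen for illustration. The documents predict no count.

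**1. The plan's own figure.** The text reads "Although testing efficacy is not the primary goal, we will have 80% power to detect a standardized mean difference of" 0.9, at alpha 0.25, without saying whether the test is one- or two-sided. With n = 10 per group:
- Noncentrality = d × √(n/2) = 0.9 × √5 = 2.01.
- Two-sided alpha 0.25: power 80.6% (normal approximation) or 79.6% (exact t).
- One-sided alpha 0.25: 91.0% or 90.7%.

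The stated 80% reproduces as a two-sided test. It concerns a mean difference only. The plan has no corresponding figure for safety.

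**2. What an event-free arm would show.** The exact (Clopper-Pearson) upper limit for 0 of n is 1 − 0.05^(1/n) for one-sided 95% and 1 − 0.025^(1/n) for two-sided 95%.

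| Event-free participants | One-sided 95% | Two-sided 95% |
|---|---|---|
| 10 (NMES-RT/rowing arm) | 25.9% | 30.8% |
| 9 (one dropout) | 28.3% | 33.6% |
| 8 (two dropouts) | 31.2% | 36.9% |
| 20 (vitamin D, both arms) | 13.9% | 16.8% |

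The two columns are limits at different confidence levels, not the ends of a range. One event in 10 gives a two-sided interval of 0.3% to 44.5%.

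**3. Chance of seeing nothing.** P(0 of 10) = (1 − p)^10.
- True risk 5%: 0.95^10 = 0.599, so no event 60% of the time.
- True risk 10%: 0.90^10 = 0.349, so no event 35% of the time.

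**4. Size needed for a tighter limit.** Solving (1 − 0.10)^n ≤ 0.05 gives n = 29. With 0.025 on the right, n = 36. An upper limit of 10% would therefore need about three times the planned arm, all event-free.

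**5. Does session count help?** Twice weekly over about 39 weeks (9 × 52/12) is 78 sessions each, or 780 in the arm. These are repeated exposures of the same 10 people, and fracture risk depends on each person's bone. They cannot be treated as 780 independent observations of risk.

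**The case against.** **A small arm is not an error in a pilot.** This stands. Any 10-person arm gives the limits above. The fault lies in pairing that size with a goal of ensuring safety.

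**The goal sentence may be about conduct.** It is one line in a recruitment section and could mean only that procedures will be carried out carefully. That reading is possible for the safety half. It does not explain the effectiveness half, which still conflicts with the Sample Size Justification.

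**Safety is monitored.** This also stands, and a reader might wrongly infer that falls or pressure rises go unrecorded, or that no usable safety figures will exist. The documents do not support that:
- Blood pressure is taken three times per session (Blood Pressure Monitoring), and a rise of more than 20 mmHg above resting suspends the session (Protection Against Risk).
- Skin is inspected at each session and after electrode removal.
- Participants are urged to report any perceived problem, and files are reviewed every ten days.
- The IRB receives an annual adverse-event summary, and a board with stopping authority meets every six months.
- Calcium, 25(OH)D and renal values are measured and could fall under the promised summaries of all study variables.

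What remains is narrower. None of this is tied to a named safety analysis, and classification as an adverse event still passes through an opinion.

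**No passage says that zero events will be reported as proof of safety.** Correct. The forward-looking passages on guidelines and wider benefit are conditional and concern bone loss, and the Benefits section calls the study pilot work. Misuse of an event-free result is a risk created by the goal's wording, not a stated intention.

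**Conclusion.** The point holds in limited form. The stated primary goal contradicts the pilot rationale, and 10 treated participants cannot deliver it: even with no events, a true risk of up to 25.9% (one-sided 95%) or 30.8% (two-sided 95%) would remain compatible with the data. These figures assume that all 10 complete follow-up and count each person once per event type. Dropout widens the limits.

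The opinion-based definition, applied by investigators who know the arm, means that events may be counted differently between arms. The documents do not allow the direction or size of any such difference to be estimated. The missing adverse-event table would, on its own, be only a missing detail. It matters here because safety is named in the primary goal.

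It would go too far to conclude that the trial lacks safety assessment or is too small for a pilot.

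**What to change.** 1. In Detailed Strategies for the Recruitment Plan, restate the goal as describing feasibility, safety events and effect sizes, consistent with the Sample Size Justification.
2. In Adverse Events, require named events to be recorded in the session records of both arms, whether or not they are judged harmful: fracture, fall, dysreflexia or a blood pressure rise above the protocol's existing limit, and skin injury. Investigator judgement of harm and relatedness can be kept as a separate field.
3. In the Data Analysis Plan, add one descriptive table of participants with each named event, by arm and by phase (months 0 to 4.5 and 4.5 to 9), with exact 95% intervals. State that absence of events will not be presented as evidence of safety.

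**Cost.** Protocol wording, one table and a short addition to session records. The protocol describes no existing session log, so a simple form may have to be created. The downside is a less favourable stated goal. No dose, schedule or stopping rule changes.
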